4.4.1.2.5 Duration

Duration is derived from the start and end dates of the unsolicited AE:

- end date of unsolicited AE – start date of unsolicited AE + 1.

The duration is considered as missing only if one or both of the start and end dates of the unsolicited AE is missing or partially missing.

Duration period is displayed as 1-3 days, 4-7 days, 8-14 days, 15 or more, and Missing.

4.4.1.2.6 Adverse Events of Special Interest

An event will be considered as an AESI if “Yes” is checked for “Is the event an AESI?” in the eCRF.

The following AESIs will be assessed during the Acute Phases of the study:

- Acute otitis media
- Upper respiratory tract illness (URI)
 - Pharyngitis
 - Cough without LRI
- Lower respiratory tract illness (LRI)
 - Stridor
 - Rales
 - Tachypnea
 - Acute wheeze
 - Pneumonia
 - Laryngotracheobronchitis

4.4.1.2.7 Medically Attended Adverse Events

An event will be considered as an MAAE if “Yes” is checked for “Is the event an MAAE?” in the eCRF.

4.4.1.2.8 Serious Adverse Events

An event will be considered as a serious event if “Yes” is checked for “Serious” in the eCRF.

SAEs will be analyzed throughout the study using the following periods:

- Within 28 days after vaccination
- During the study (i.e., all SAEs occurred during the study)

4.4.1.2.9 Adverse Events Leading to Study Discontinuation

A flag is available in the clinical database for all AEs in order to identify AEs leading to study discontinuation.

The items that are counted are:

- Disposition table: A participant who, on the “Completion at End of Study” form question “What was the participant's status?” has “Adverse Event” checked.
- Safety overview table: A participant who has either on the “Completion at End of Study” form question “What was the participant's status?” has “Adverse Event” checked, or lists a solicited AE that has “Caused Study Termination” checked that is at least Grade 1 or an unsolicited AE that has “Caused Study Discontinuation” checked that is at least Grade 1 or missing and is within the time period indicated.
- System Organ Class (SOC)/Preferred Term (PT) table: A solicited AE that has “Caused Study Termination” checked that is at least Grade 1 or an unsolicited AE that has “Caused Study Discontinuation” checked that is at least Grade 1 or missing and is within the time period indicated.

4.4.1.3 Solicited and Unsolicited AEs after any vaccination

This section is applicable for tables which present results after any vaccination.

The rules for calculation are to select the worst case:

- Maximum intensity: Select the maximum overall intensity for any vaccination
- Time of onset: Select the minimum time of onset for any vaccination
- Duration (for unsolicited AE): Select the maximum duration for any vaccination

4.4.2 Immunogenicity

4.4.2.1 Computed Values for Analysis

In order to appropriately manage extreme values (< lower limit of quantification [LLOQ] and \geq upper limit of quantification [ULOQ]) for analysis purposes, the following computational rule is applied to the values provided in the clinical database for each blood sample drawn:

- If a value is < LLOQ, then use the computed value LLOQ/2
- If a value is between \geq LLOQ and < ULOQ, then use the value
- If a value is \geq ULOQ, then use the computed value ULOQ

For the RSV serum anti-F IgA antibodies, we will consider the LOD value (██████████) for the calculation instead of the LLOQ.

Note for titers converted into IU/mL:

The IU/mL is computed using the following calibration formulae:

$$\text{IU/mL} = \frac{\text{Sample Titer}}{(\text{Assay calibrator})/\text{Assigned Potency}} = \frac{\text{Sample Titer}}{(\text{Assay calibrator})/\text{Assigned Potency}}$$

Where:

- *Sample Titer*: This is the titer directly observed from the sample using one plate.
- *Assigned Potency*: The established internal reference standard and replacement for International
- *Assay calibrator*: Each plate will also measure the titer of the reference standard

Because of this calibration formula, LLOQ related to titers can be calibrated to different IU/mL depending on the observed titer of calibrator (international reference or in-house reference); so titer < LLOQ is not consistent converting to IU/mL from run to run.

As a consequence, for any value reported as “< X”, we use the computed value X/2. No ULOQ is defined.

4.4.2.2 Fold-rise

For calculation of fold-rise and geometric mean titer ratio (GMTR) a titer reported as < LLOQ will be converted to $\frac{1}{2}$ LLOQ for a numerator and will be converted to LLOQ for a denominator. If both numerator and denominator are < LLOQ, then both will be converted in the same way so that titer ratio=1. This rule is used to minimize the numerator and maximize the denominator as a conservative approach.

For the RSV serum anti-F IgA antibodies, we will consider the LOD value (██████████) for the calculation instead of the LLOQ.

If the computed value is \geq 4-fold rise, then the derived \geq 4-fold rise indicator will be “Yes” for that test, otherwise \geq 4-fold rises will be “No”.

Note: If either numerator or denominator is missing, then fold-rise computed value/indicator is missing.

Note for titers converted into IU/mL: This rule would apply using X instead of LLOQ.

4.4.2.3 Baseline serostatus

For this Sanofi Phase I/II trial, baseline serostatus will be determined from serum samples collected at baseline (V01). Participants will be categorized into RSV-experienced or RSV-naïve based on the presence or absence of detectable RSV serum anti-F IgA antibodies. This biomarker has been chosen since it is produced only in response to RSV infection and not transferred transplacentally from mother to child. Baseline serostatus will be determined as follows:

- ***RSV-naïve*** for participants with baseline IgA titer [REDACTED]
- ***RSV-experienced*** for participants with baseline IgA titer [REDACTED]
- ***Undetermined*** for participants with baseline IgA titer ‘missing’ or ‘NR’.

4.4.3 Efficacy

The following events will be collected in the database during illness visits:

- Fever
- Acute otitis media
- Upper respiratory tract illness:
 - Rhinorrhea
 - Nasal congestion
 - Pharyngitis
 - Cough without LRI
- Lower respiratory tract illness
 - Stridor
 - Rales
 - Tachypnea
 - Acute wheeze
 - Pneumonia
 - Laryngotracheobronchitis

A diagnosis of RSV MAARI requires the documentation of any of the events described above, associated with a respiratory sample positive for RSV by [REDACTED].

A diagnosis of RSV MAALRI (a subset of MAARI) requires the documentation of any of the lower respiratory tract illness events described above, associated with a respiratory sample positive for RSV by [REDACTED].

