Based on previous data regarding the seasonality of RSV in the US, Canada, Chile, Honduras, and South Africa, surveillance for RSV-associated disease will be largely conducted during the NH (1st November to 31st March) and SH (1st May to 30 September) RSV seasons respectively, adjusted for local site RSV seasonality. Due to the disruption of the seasonal pattern of RSV globally (24) (25), it is unclear when the normal seasonal transmission will resume though there is some suggestion of a rebound in the winter of 2021–2022 in the NH (26). Because of the unpredictability of the RSV season due to the impact of COVID-19 nonpharmaceutical interventions, study participant enrollment and vaccination will continue regardless of RSV activity. Study participants enrolled before the routine winter RSV season for that locality will be followed up until the consequent month after the end of the routine season (i.e. April for NH and October for SH). Study participants enrolled during the routine RSV season (i.e. November to March for NH and May to September for SH) will be followed up for at least 5 months after the last vaccine administration. During the RSV season or post-vaccination RSV surveillance, study participants will be monitored for symptomatic medically attended respiratory illness. Note, this surveillance may overlap with the Acute and Post-Acute phases. In this case, evaluations required for each of the relevant phases of the study will be conducted.

Evaluation of two vaccine doses [REDACTED]:

Previous Phase Ia studies done by the NIH have demonstrated that the [REDACTED] dose of RSV ΔNS2/Δ1313/I1314L vaccine resulted in better infectivity and neutralizing antibody seroresponse than the [REDACTED] dose, with no evidence of an excess of respiratory tract illness associated with receipt of the higher dose ([REDACTED]). However, in these studies, the vaccine was administered intranasally using a sterile, needle-less 1 mL oral syringe, at a volume of 0.5 mL as nasal drops (approximately 0.25 mL per nostril). In VAD00001 study, the vaccine would be administered at a total volume of [REDACTED] [REDACTED] [REDACTED]

Use of an intranasal [REDACTED]
may improve the overall delivery of the vaccine and may increase replication in both doses. Use
of the [REDACTED] may also improve the infectivity of the low dose [REDACTED]
doses will be the minimal doses explored using the [REDACTED]

Evaluation of two administrations of vaccine doses:

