9.1.1.3.4 Medically Attended Adverse Events

Any MAAEs occurring within the first 28 days post-vaccination (D0 to D28 for all participants in Cohorts 1, 2, 3 and 4 and D56 to D84 for participants in Cohorts 2 and 4) will be collected using the same process as other AEs. Medically attended acute respiratory illness (MAARI) and medically attended acute lower respiratory illness (MAALRI) events occurring within this time frame and outside the RSV surveillance season will be classified as MAAEs.

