9.2.1.3 Safety Assessment Methods

Shedding of the attenuated RSV vaccine strain in nasal swab samples will be evaluated by RSV quantitative Reverse Transcriptase Polymerase Chain Reaction [REDACTED], which can specifically detect and quantify RSVt Δ NS2 vaccine strain (RSV Δ NS2/ Δ 1313/I1314L) in human nasal swab samples. Based on the evaluation of precision (intra-assay and intermediate precision), dilutional accuracy, linearity, and specificity, RSVt [REDACTED] is suitable for clinical testing of human nasal swab samples in support of the development of RSV Vaccine candidates.

RSVt NS2 [REDACTED]

The RSVtNS2 [REDACTED] will be performed at Sanofi Pasteur GCI, Swiftwater, PA or at a qualified contract laboratory for GCI.

The RSVtNS2 [REDACTED] will be used to measure virus shedding from nasal swab samples from study participants. Development and qualification of this method is completed; this method will be validated prior to Phase III clinical testing.

RSVt NS2 [REDACTED] *Description*

To quantify viral shedding in infants vaccinated with RSV Δ NS2/ Δ 1313/I1314L (RSVt) vaccine, a [REDACTED] was developed that would specifically detect and quantify RSV Δ NS2 candidate in nasal swab samples. Beyond the deletion of the NS2 gene, there are few sequence differences between RSV Δ NS2/ Δ 1313/I1314L vaccine and wt RSV A.

RSVt [REDACTED] was designed using the Light Cycler Probe system from Sigma. This system consists of two hybridization probes that are designed so that they bind the target 1-5 nucleotides apart. Probe 1 (donor) is labeled on the 3' end with a donor reporter. Probe 2 (acceptor) is labeled at the 5' end with an acceptor reporter. During the annealing step, the [REDACTED] primers and the LightCycler Probes hybridize to their specific target regions, bringing the probes in proximity. When this happens, the donor dye is excited by the LightCycler, and energy is transferred from the donor to the acceptor dye. The acceptor reporter's emission is detected by the Light Cycler at 640 nm.

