9.3.4.2 Efficacy Assessment Methods

[figure not shown]
The method for the exploratory efficacy endpoints is the [REDACTED], an automated qualitative nucleic acid multiplex *in vitro* diagnostic test designed to simultaneously detect and identify multiple respiratory viral and bacterial nucleic acids in NS samples.

[REDACTED] Method:

The ePlex system which is used to run the [REDACTED] is a closed system that automates all aspects of nucleic acid testing including extraction, amplification, and detection. Electrowetting or digital microfluidics use electrical fields to manipulate droplets on the surface of a

hydrophobically coated printed circuit board (PCB). Samples and reagents are moved in a programmable fashion in the ePlex cartridge to complete all portions of the sample processing. Nucleic acid extraction from biological samples occurs within the cartridge via cell lysis, followed by nucleic acid capture onto magnetic beads and release for [REDACTED] amplification. Thereafter, exonuclease digestion creates single-stranded DNA in preparation for eSensor detection. eSensor technology is based on the principles of competitive DNA hybridization and electrochemical detection, which is highly specific and is not based on fluorescent or optical detection. Competitive DNA hybridization: the single-stranded target DNA binds to a complementary, single-stranded capture probe, immobilized on the working gold electrode surface. The single-stranded signal probes (labeled with electrochemically active ferrocenes) bind to a specific target sequence/region adjacent to the capture probe. Simultaneous hybridization of the target to signal probes and capture probe is detected by alternating current voltammetry (ACV). Each working electrode on the array contains specific capture probes, and the sequential analysis of each electrode allows for the detection of multiple analyte targets.

The [REDACTED] is a qualitative assay. It will only indicate the presence or absence of a viral or bacterial target in a nasal swab sample collected in viral transport medium (VTM) and will not be used to calculate a viral titer. The [REDACTED] can detect and distinguish between sixteen respiratory viral targets and two respiratory bacterial targets as shown in Table below.

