5.1.1.2 Statistical Methods

The data for any participant infected by laboratory confirmed wt RSV will be excluded from immunogenicity and viral shedding analyses from the date of wt RSV infection.

A short complementary analysis will be done without the exclusion of data to compare results.

Safety

Solicited adverse reactions (ARs), unsolicited AEs (including SAEs), MAAEs and AESIs will be summarized as described in Table 5.1. The main parameters will be described with 95% CI. At least the following parameters will be presented by vaccine group after each and any vaccination, in all participants regardless of baseline serostatus:

- Unsolicited systemic AEs occurring within 30 minutes of administration (immediate unsolicited AEs)

- Solicited administration site reactions and solicited systemic reactions within 28 days after each and any administration according to presence, time period, time of onset, intensity, number of days of presence, action taken, and whether the reaction led to early termination from the study. When more than 1 intensity level is reported within a time period, the highest intensity will be used.
- Unsolicited AEs occurring within 28 days after each and any administration by system organ class (SOC) and preferred term (PT), relationship, intensity, time of onset, duration and whether the AE led to early termination from the study.
- All SAEs that occur throughout the study by SOC and PT, seriousness criteria, time of onset, outcome, relationship, and whether the SAE led to early termination throughout the study
- All MAAEs and AESIs reported within 28 days after each and any vaccination by SOC and PT and relationship

Bayesian approach

A Bayesian approach based on Posterior Distribution may be applied to assess the difference between each RSV formulation and placebo group on the following safety endpoints (and/or other endpoint of interest):

- Any Grade ≥ 3 LRI
- Grade 3 fever

The probability that the difference of percentages of events between one RSV formulation and Placebo is greater than a pre-specified margin (δ) can be calculated based on posterior distribution, using non-informative prior Beta (1,1) (3) and observed binomial data:

Proba (%RSV - %Placebo > δ)

With:

- %RSV = (number of events / number of participants) in RSV group
- %Placebo = (number of events / number of participants) in Placebo group

If this probability is high (e.g., $\geq 80\%$) then it may be recommended to drop the formulation.

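### The RSV MAARI/MAALRI definition has no wild-type requirement, so shed vaccine virus can be counted as RSV disease in the vaccine arms and lower the exploratory VE

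*SAP*

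**What the plan says.** **Case definition.** SAP 4.4.3 lists fever, otitis media, upper respiratory and lower respiratory findings collected at illness visits, then states: "A diagnosis of RSV MAARI requires the documentation of any of the events described above, associated with a respiratory sample positive for RSV". MAALRI is the same with a lower respiratory finding. Protocol 9.3.4.1 adds that the findings come from a documented physical examination. Neither text requires the virus to be wild-type.

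**Assay.** Protocol 9.3.4.2 describes "an automated qualitative nucleic acid multiplex" test and says of the panel: "It will only indicate the presence or absence of a viral or bacterial target in a nasal swab sample collected in viral transport medium". On the vaccine strain compared with wild-type RSV A, Protocol 9.2.1.3 says: "Beyond the deletion of the NS2 gene, there are few sequence differences between RSV". The same section describes an assay aimed at the NS2 deletion site that gives no signal with wild-type RSV A. Its stated use is measuring shedding; it is not named as a step in classifying illness swabs.

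**Timing.** Protocol 5.1.1 lets Cohort 4 be dosed at any time of year, including the RSV season. Protocol 9.1.1.1 ties the 28-day Acute Phase to the duration of shedding. Protocol 5.1.2 says of Cohort 4: "Note, this surveillance may overlap with the Acute and Post-Acute phases". Protocol 9.1.1.3.4 makes one carve-out for MAARI and MAALRI within 28 days of a dose: "events occurring within this time frame and outside the RSV surveillance season will be classified as MAAEs".

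**Exclusions.** SAP 5.1.1.2 states: "The data for any participant infected by laboratory confirmed wt RSV will be excluded from immunogenicity and viral shedding analyses", from the date of infection, and plans a short complementary analysis without that exclusion. SAP 5.2.3 removes from the PPAS a child with a confirmed diagnosis of wild-type RSV before the post-vaccination blood sample. Neither document says how wild-type is confirmed.

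**The concern.** A live vaccine virus that is shed can be picked up by a test for RSV. If a child sheds it while attending for an ordinary cold or fever in season, the written rule has both elements of a case: a listed finding and an RSV-positive sample. Fever, rhinorrhea and nasal congestion are on the SAP list and are also solicited reactions to the vaccine, so the two elements can occur together without any wild-type infection. The carve-out to MAAE does not help, because it covers only events outside the season, whereas SAP 5.1.3 summarizes illness collected during the season.

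Placebo recipients are not given vaccine virus, so the misclassification is one-sided: it adds cases to the numerator of VE in the low- and high-dose arms only.

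Two related gaps share the cause. The undefined term for confirmed wild-type RSV decides whose data enter the primary immunogenicity analysis. In addition, the exclusion names immunogenicity and shedding but not infectivity. There, a 4-fold rise by D56 or D84 counts as vaccine infection, whereas Protocol 5.1.1 reads a 4-fold rise over the season as wild-type infection missed by surveillance.

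**Working it through.** **The plan's own figure.** The only precision statement is a 95% chance of seeing at least one event, at 3% incidence with n = 100 and at 3.75% with n = 80. These reproduce: 1 - 0.97^100 = 95.2% and 1 - 0.9625^80 = 95.3%. The present point does not depend on them.

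**Where shedding can meet in-season surveillance** (dates from Protocol 5.1.5; season starts of 1 November and 1 May):

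- Cohort 1: doses from 4 to 27 October 2020; the last D28 is 24 November.
- Cohort 2: second doses from 3 to 26 April 2021; the last D28 is 24 May.
- Cohort 3: none; the last dose is 31 May 2021, with D28 on 28 June.
- Cohort 4: any dose in, or within 28 days before, the season.

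**VE lost per false case.** SAP 5.1.3 gives VE = 1 - (C_RSV/N_RSV)/(C_P/N_P). One extra case in the vaccine arm changes VE by -100 × N_P/(N_RSV × C_P) points:

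- Cohort 4 alone (60 vs 60): 100/C_P.
- Low dose pooled (100 vs 120): 120/C_P.
- High dose pooled (80 vs 120): 150/C_P.

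For Cohort 4, assumed placebo attack rates of 5, 10 and 15% give C_P = 3, 6 and 9, so each false case costs 33.3, 16.7 or 11.1 points.

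**Example, Cohort 4**, assuming 6 placebo cases and 3 true vaccine-arm cases (true VE 50%), with the SAP's exact conditional interval:

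| False cases | VE | 95% CI |
|---|---|---|
| 0 | 50% | -134% to 92% |
| 1 | 33% | -181% to 86% |
| 2 | 17% | -228% to 80% |
| 3 | 0% | -274% to 73% |

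Pooled, assuming 12 placebo cases, three false cases take the low dose (5 true cases) from 50% (-53% to 86%) to 20% (-113% to 72%), and the high dose (4 true cases) from 50% (-65% to 88%) to 12.5% (-141% to 71%).

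**How many false cases?** The documents give no rate. Assume 5-10% of 60 children have a qualifying illness in a 28-day window and 30-60% of those swabs carry vaccine RNA. Then 60 × 0.05 × 0.30 = 0.9 and 60 × 0.10 × 0.60 = 3.6, but only if every child's whole window lies inside surveillance. If first doses were spread evenly over the year and 5 of 12 months are in season, this becomes 0.9 × 5/12 = 0.4 to 3.6 × 5/12 = 1.5 per arm. At C_P = 6 that is about 6 to 25 points. The second dose should add less, since Protocol 5.1.2 reports that replication after a second administration was generally highly restricted.

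**Infectivity.** With true vaccine infection p and wild-type infection w, and every wild-type infection giving a 4-fold rise and escaping exclusion, the observed proportion is p + w(1 - p). Assuming p = 50% and w = 10% or 20%: 0.50 + 0.10 × 0.50 = 55%, and 0.50 + 0.20 × 0.50 = 60%. Placebo would show 10% or 20%. This is an upper bound, because detected wild-type cases may be excluded.

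**The case against.** **Removal as wild-type.** A reader might infer that any RSV-positive panel result removes a vaccinee from the immunogenicity analysis. The text does not support that: Protocol 12.2.1 and SAP 5.1.1.2 require laboratory confirmation of wild-type RSV, and the PPAS rule a confirmed wild-type diagnosis. Nothing links a MAARI positive to either. The planned analysis without the data exclusion would also expose a large effect. What remains is that the confirming test is undefined.

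**The assay is partly unseen.** The assay name is redacted and the panel's target table is not shown. The RSV detection method at illness visits (Protocol 5.1.4.1) is not specified either. The ad hoc IDMC, if convened, is to consider whether an event coincides with vaccine shedding (Protocol 5.1.6), so vaccine-specific data on ill children may exist. Panel detection of the vaccine strain is therefore an inference, and typing may already be intended. The case definition still does not use it.

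**Overlap is limited.** Saying that any illness after vaccination becomes a case would be wrong. A listed finding is needed and, by the endpoint's name, medical attendance. Out-of-season acute-phase events go to MAAE. In Cohorts 2 and 4 the fortnightly season calls run only from Visit 05 to Visit 06, after both 28-day windows. This narrows the problem but does not close it: acute-phase contacts are more frequent than the season calls, and Protocol 5.1.2 says both sets of evaluations are done when phases overlap.

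**Infectivity.** Its inputs are swab detection and fold-rise, so the exclusion can be read as covering it, and results by group show the placebo background. That reading is reasonable but unstated, and wild-type infections that go undetected would remain in any case.

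**Importance.** Efficacy is exploratory, no hypothesis is tested, and dose selection rests on safety, infectivity and immunogenicity. In the worked example the VE interval is very wide even with no false cases. This stands and sets the severity.

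**Conclusion.** The definition as written can count shed vaccine virus as RSV disease, in vaccine arms only, and so biases the exploratory VE downward. The exposure is mainly in Cohort 4, with a few late-dosed children in Cohorts 1 and 2 and none in Cohort 3. The loss per false case (100/C_P points in Cohort 4) follows from the SAP's formula. The number of false cases, the attack rates and the true VE of 50% are assumptions, and the mechanism requires that the panel detects the vaccine strain.

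The secondary gaps also hold: the undefined wild-type term controls the FAS data exclusion and PPAS membership, and the exclusion does not name infectivity. It would be tempting to conclude that the primary immunogenicity results are biased by loss of good responders. The documents show only that the rule is open to misclassification, not that this happens.

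Severity is moderate. The VE estimate should not be read without this correction, but no primary conclusion depends on it.

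**What to change.** 1. **SAP 4.4.3.** Test RSV-positive illness swabs collected within 28 days of a dose with the existing NS2-deletion assay. Count a wild-type RSV MAARI/MAALRI when the swab is RSV-positive and vaccine-strain-negative, or RSV B-positive where subtype is available. Report vaccine-strain-positive swabs separately as indeterminate, and show VE with and without them. Simply dropping them is not safe: the assay cannot rule out wild-type RSV A co-infection, so the loss would fall on vaccine arms only and push VE upward.
2. **SAP 5.1.3.** Add a VE analysis, in all arms including placebo, counting only cases with onset from day 29 after each dose. It needs no laboratory work.
3. **SAP 5.1.1.2 and 5.2.3.** Use the same wild-type definition for the data exclusion and the PPAS, and keep the planned analysis without exclusion.
4. **SAP 5.1.2.2.** State that the wild-type exclusion also applies to infectivity. Present infectivity as the difference from concurrent placebo with the Wilson score interval already in SAP 5.1.1.2, since undetected wild-type infections would remain. Under the model above this difference is p(1 - w), that is 45% or 40% when p is 50%, so it errs low and should be shown beside the raw proportions.

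Cost: SAP wording, a few extra runs of an assay already in use, a slight delay in classifying cases, and fewer cases in the day-29 analysis. If typing is already intended, stating it in SAP 4.4.3 covers item 1.
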